5.9.6 Pregnancy of Female Partners of Male Patients

Male patients will be instructed that if their partner becomes pregnant during the study and up to [REDACTED] after the last dose of study drug, this should be reported to the Investigator.

If a male patient's female partner becomes pregnant, the pregnancy must be reported to the Sponsor (or designated service provider) as soon as possible. Consent should be obtained from the pregnant partner in order to collect further information.

All pregnancies will be followed until delivery or the end of pregnancy (i.e., delivery, still birth, miscarriage), provided consent is obtained. The mother and child exposed *in utero* will also be followed for [REDACTED] after the birth, provided consent is obtained.

5.10 Total Blood Volume

5.11 [REDACTED]

The image consists of several horizontal black bars of varying lengths, separated by white spaces. The bars are positioned at different heights within the frame. The top and bottom edges of the image are heavily redacted with large black blocks. The overall appearance is like a series of horizontal steps or a bar chart.

6 INVESTIGATIONAL PRODUCTS

6.1 Dosage and Administration of ONO-7475

ONO-7475 will initially be dosed once daily. Posology may be modified based on emerging safety PK and PD data (see Sections 3.1.2 and 3.1.3).

ONO-7475 will be administered as an oral tablet or as a combination of multiple oral tablets [REDACTED] ONO-7475, which are packed in bottles.

[REDACTED]

[REDACTED]

[REDACTED]

[REDACTED]

6.1.1 Assessment of the Effect of Food on the Pharmacokinetics of ONO-7475 (Part A)

In this part of the study, the effect of food on the PK of ONO-7475 will be evaluated.

6.2 Dosage and Administration of Venetoclax

In Part D only: venetoclax will be administered orally with food and water. The dose will be made up of tablet(s) containing 10, 50 and/or 100 mg venetoclax which are packed in bottles or blisters.

The dose of venetoclax must be titrated for the first 3 days of dosing in Cycle 1 (ramp-up period) according to Table 3 to minimize the risk of tumor lysis syndrome prior to dosing with the maintenance dose. During the ramp-up period, prophylactic measures including adequate hydration and anti-hypouricemic agents should be considered according to the site's standard procedures. Patient's blood chemistry parameters will be monitored (e.g., potassium, uric acid, phosphorus, calcium and creatinine) at pre-dose, 6–8 hours after each new dose during ramp-up period (i.e., Day 1, 2, 3 and 4 in Cycle 1) and 24 hours after reaching final dose (i.e., Day 5 in Cycle 1) (see Section 5.9, Section 13.3, and Section 13.4). Hospitalization during ramp-up period is recommended if appropriate.

6.3 Treatment Assignment

Patients will be assigned to treatment groups for each dose cohort and will be assigned ONO-7475 treatment kits via the interactive web response system. The

Study Number: ONO-7475-01 Protocol	Version: 10.0 [incorporating Amendments #1–9]
--	--

same process will apply for those patients who have their dose increased (or decreased).

6.4 Packaging and Labelling

All packaging and labels will be prepared in accordance with 21 Code of Federal Regulations 312.6 – Labelling of an investigational new drug and any local regulatory requirements.

6.5 Preparation of Investigational Drugs

ONO-7475

No further preparation of ONO-7475 tablets is needed.

Venetoclax

No further preparation of venetoclax tablets is needed.

6.6 Handling and Storage

ONO-7475 should be stored [REDACTED] and a temperature log will be maintained during the conduct of the study. All study drugs must be stored in a secure location and may only be dispensed by the Investigator or by a member of staff who is authorized by the Investigator, or by a pharmacist, as appropriate.

Venetoclax should be stored as per the approved label of VENCLEXTA²².

6.7 Product Accountability and Assessment of Compliance

In accordance with GCP, all supplies of ONO-7475 and venetoclax will be accounted for by the investigational site.

The dispensing and return of the study drug will be carefully recorded on appropriate drug accountability forms and an accurate accounting will be available for verification and assessment of compliance by the clinical research associate at each monitoring visit.

Investigational product accountability records will include:

- Details of receipt
- Storage
- Administration, and
- Return or destruction

The unit of accountability for the study is 1 tablet. At the end of the study, following full accountability and reconciliation, the Sponsor will provide instruction for all

unused study drugs to be destroyed. A certificate of destruction will be supplied to the Sponsor.

6.8 Treatment of Investigational Product Overdose

ONO-7475

At this stage in development, no specific treatment for overdose has been identified and the physician is advised that there is no specific antidote. Supportive measures to maintain the patient's vital functions should be implemented and patient should be carefully monitored. Any event of overdose should be reported as a SAE by the Investigator (or designee) to the Sponsor immediately, in accordance with Section 9.2.2.

Venetoclax

In the event of overdose, the patient should be monitored (including relevant blood counts) and should receive supportive treatment, as necessary. There is no known specific antidote for venetoclax overdose.

7 CONCOMITANT MEDICATIONS AND NON-DRUG THERAPIES

7.1 Permitted Medications and Supportive Therapies

Country	Percentage (%)
United States	13.4
Canada	14.8
United Kingdom	16.0
Germany	16.7
France	17.1
Italy	17.5
Spain	17.8
Portugal	18.1
Greece	18.4

7.2 Prohibited Medications

The figure consists of a 5x5 grid of black rectangles on a white background. The rectangles are arranged in a staggered pattern: the first row has 1 rectangle, the second row has 2 rectangles, the third row has 3 rectangles, the fourth row has 4 rectangles, and the fifth row has 5 rectangles. The rectangles are black and have a thin white border. The grid is centered on a white background.

7.3 Medications to be Used with Caution

[REDACTED]

As per the prescribing information for VENCLEXTA²², the safety and efficacy of immunization with live attenuated vaccines during or following VENCLEXTA therapy have not been studied. The Investigator should advise patients that vaccinations may be less effective.

8 PATIENT COMPLETION AND WITHDRAWAL

8.1 Patient Completion

Any patients who are continuing to receive study drug at the time of final data cut-off (i.e., those who have not previously withdrawn) will be deemed as having completed the study.

If a patient withdraws from the study during the treatment period, every attempt should be made for the patient to attend the safety follow-up visit, which will represent the end of the patient's participation in the study, and to provide information of survival status. If the patient does not agree to have the safety follow-up, only survival data will be collected. The last clinic visit will be considered the final study visit for the patient (i.e., the patient completion/withdrawal date). If a patient refuses a safety follow-up visit after withdrawing from the study, the last contact date with the patient will define the patient completion/withdrawal date.

8.2 Study Completion

The study will be regarded as completed, once the last patient has attended their last study visit. The study may be terminated by the Sponsor at any stage. If the study is halted, the reasons for doing so will be provided to the Investigator and the patients. The regulatory authorities will also be notified according to local regulations. For those patients who are already enrolled into the trial, their treatment regimen will be provided until disease progression, or until patient withdrawal due to development of an unacceptable toxicity or patient withdrawal of consent.

8.3 Patient Withdrawal

8.3.1 Patient Withdrawal from Study

In accordance with the Declaration of Helsinki, a patient has the right to withdraw from the study at any time without giving a reason.

The reasons for protocol-specified patient withdrawal are as follows: withdrawal by patient (informed consent withdrawn or patient requests discontinuation from the study); Investigator decision; DLT or progressive disease.

In cases where a female patient becomes pregnant, the decision of whether or not to withdraw the patient from investigational product will be taken locally at site level and handled on a case-by-case basis.

8.4 Screen and Baseline Failures

Data for all study visits will be recorded on the eCRF for patients who receive study drug treatment. Only minimal data (i.e., demography and reasons for screen failure) will be recorded on the eCRF for patients who fail inclusion/exclusion criteria and/or do not receive study drug. Further data, such as AEs, will not be collected from patients once they are considered screen failures or have decided to withdraw prior to receiving study drug.

9 ADVERSE EVENTS AND SERIOUS ADVERSE EVENTS

9.1 Adverse Events

An AE is any untoward medical occurrence in a patient or clinical investigation patient administered a pharmaceutical product and which does not necessarily have a causal relationship with this treatment. An AE can therefore be any unfavorable and unintended sign (including an abnormal laboratory finding), symptom, or disease temporally associated with the use of a medicinal (investigational) product, whether or not related to the medicinal (investigational) product.

9.1.1 Adverse Event Severity

Each AE must be rated in intensity according to NCI CTCAE criteria version 4.03.

The NCI CTCAE, version 4.03, grades refer to the severity of AEs. The NCI CTCAE displays Grades 1 through 5 with unique clinical descriptions of severity for each AE based on the general guideline presented below:

- Grade 1 Mild; asymptomatic or mild symptoms; clinical or diagnostic observations only; intervention not indicated.
- Grade 2 Moderate; minimal, local or non-invasive intervention indicated; limiting age-appropriate instrumental activities of daily living.
- Grade 3 Severe or medically significant, but not immediately life threatening; hospitalization or prolongation of hospitalization indicated; disabling; limiting self-care activities of daily living.
- Grade 4 Life-threatening consequences; urgent intervention indicated.

Grade 5 Death related to AE.

9.1.2 Adverse Event Relationship to Investigational Product(s)

The Investigator must classify the relationship of the AE to ONO-7475 (both Parts) and venetoclax (Part D only).

The possible relationships for Part A are:

- | | |
|----------------------------------|--|
| Not related/
unlikely related | The temporal sequence between the AE and drug administration is such that the drug is not likely to have had any reasonable association with the observed event; or underlying disease, other drugs or chemicals provide plausible explanations. |
| Possibly related | 
The AE follows a reasonable time relationship from drug administration;
 
and
 
The AE could also be explained by concurrent disease or other drugs or chemicals.
 
Note: Information on drug withdrawal may be lacking or unclear.
 |
| Probably related | 
The AE follows a reasonable time relationship from drug administration;
 
The AE is unlikely to be attributed to concurrent disease or other drugs or chemicals;
 
and
 
Follows a clinically reasonable response upon withdrawal (dechallenge);
 
Note: rechallenge positive data are not required to fulfill this definition.
 |
| Definitely related | 
The AE follows a reasonable time relationship from drug administration (i.e., occurs in a plausible time relationship to drug administration);
 
The AE cannot be explained by concurrent disease or other drugs or chemicals;
 |

The AE abates or follows a clinically reasonable response upon withdrawal (dechallenge positive);

and

The AE is confirmed by reappearance of the reaction on repeat exposure (rechallenge positive).

The possible relationships for Part D are:

- | | |
|-------------|---|
| Not related | The temporal sequence between the AE and drug administration is such that the drug is not likely to have had any reasonable association with the observed event; or underlying disease, other drugs or chemicals provide plausible explanations. |
| Related | 
The AE follows a reasonable time relationship from drug administration (i.e. occurs in a plausible time relationship to drug administration);
 
The AE cannot be explained by concurrent disease or other drugs or chemicals;
 
The AE abates or follows a clinically reasonable response upon withdrawal (dechallenge positive);
 
or
 
The AE is confirmed by reappearance of the reaction on repeat exposure (rechallenge positive).
 |

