2 STUDY OBJECTIVES AND ENDPOINTS

Table 4 below outlines the primary, secondary, and exploratory objectives of the study and their associated endpoints.

Table 4 Objectives and Endpoints for all study parts

Part A – Monotherapy Dose Escalation	
Primary Objective	Primary Endpoints
To assess the safety and tolerability of ONO-7475 monotherapy in patients with R/R AML or R/R MDS	
• Incidence, nature, and severity of AEs and serious AEs (SAEs)• Clinically significant changes in ophthalmology parameter examinations and 12-lead electrocardiogram (ECG)

Study Number: ONO-7475-01 Protocol	Version: 10.0 [incorporating Amendments #1–9]
--	--

Secondary Objectives	Secondary Endpoints
To select an optimal dose of ONO-7475 for further clinical evaluation	Maximum tolerated dose (MTD) and/or recommended pharmacological dose based on clinical response or pharmacodynamics (PD) markers
To assess the pharmacokinetics (PK) of ONO-7475 in patients with R/R AML and R/R MDS	PK parameters: maximum observed plasma concentration (Cmax), time to reach Cmax (Tmax), area under the plasma concentration-time curves (AUC) on Days 1 and 28, elimination half-life (T1/2) plasma concentration prior to next dose
To evaluate food effect on the PK of ONO-7475	The PK of the food effect on ONO-7475 (Cmax, Tmax, AUC, T1/2, and plasma concentration prior to next dose)
To assess the PD activity of ONO-7475 in patients with R/R AML and R/R MDS	PD biomarkers of response: plasma inhibitory activity (PIA) assay (pAxi/pMer inhibition)
To assess the preliminary clinical efficacy of ONO-7475 in patients with R/R AML and R/R MDS	
 Overall response rate (ORR), duration of response (DoR), event-free survival (EFS) Complete remission (CR) without minimal residual disease (MRD)

Part D – Combination with Venetoclax

Primary Objectives	Primary Endpoints
SA group: To assess the safety and tolerability of ONO-7475 in combination with venetoclax EA group: To assess the preliminary efficacy of ONO-7475 in combination with venetoclax	SA group: Incidence, nature, and severity of AEs and SAEs EA group: CR/CR with partial hematologic recovery (CRh) rate
Secondary Objectives	Secondary Endpoints

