3.1.2 Dose Escalation

3.1.2.1 Part A

The initial monotherapy dose escalation phase (Part A) will start with a dose of 3 mg ONO-7475 once daily. Dose escalation will proceed in increments not exceeding [REDACTED]. Depending on emerging PK, PD, and safety data, the posology of ONO-7475 (e.g., intermittent dosing or twice daily) may be modified. Example dose levels are shown in Table 5. The exact dose increase and number of dose levels will be based upon the review of safety and, where available, PK, PD, and efficacy data, and dose escalation will only occur after discussion and agreement between the Sponsor and members of the SRC who may recommend alternative doses to those in Table 5 based on their review. ONO-7475 will be administered in a fasted state ([REDACTED]) in all cohorts, except as outlined in Section 6.1.1.

Table 5 Proposed Dose-Escalation Plan*

Dose Level	Dose of ONO-7475
Level 1	3 mg
Level 2	6 mg
Level 3	10 mg

*May be modified based on the emerging safety/tolerability profile

[REDACTED]

[REDACTED]

[figure not shown]

A SRC will be convened to review draft safety, PK, and PD data on an ongoing basis (see Section 11.6). At the end of the dose escalation stage for Part A of the study, the SRC will recommend a dose level of ONO-7475 (MTD or OBD) to evaluate in the subsequent Part D of the study or expansion cohorts in the current part of the study, as applicable, based on available data including safety, preliminary efficacy, PK and PD. The roles, responsibilities and procedures of the SRC will be documented in a written SRC Charter. As stated above, dose escalation will proceed in increments not exceeding [REDACTED], until significant ONO-7475-related toxicity is observed, at which time the maximum allowed increase (if any) is to be reviewed by the SRC. A pre-specified plan for altering dose increases will be included in the SRC charter.

The SRC will meet at the predefined time points for study decision making and will also monitor the safety of patients throughout the study and may make recommendations at any time if there are concerns about the safety of the patients in the study.

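### Part A causality classes overlap: read literally, every adverse event that is possibly related also qualifies as not related/unlikely related

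*Combined protocol and SAP*

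**What the plan says.** Section 9.1.2 requires the investigator to classify the relationship of each AE to ONO-7475. The Part A scale has four classes: *Not related/unlikely related*, *Possibly related*, *Probably related* and *Definitely related*.

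- *Not related/unlikely related* has two limbs. The first is timing that makes an association with the drug unlikely. The second follows directly: "or underlying disease, other drugs or chemicals provide plausible explanations".
- *Possibly related* has two conditions joined by *and*: "The AE follows a reasonable time relationship from drug administration", and "The AE could also be explained by concurrent disease or other drugs or chemicals".

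Relatedness then appears in three visible places that matter for Part A:

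- Section 3.1.2.1 lets dose increments proceed up to a ceiling (redacted) "until significant ONO-7475-related toxicity is observed, at which time the maximum allowed increase (if any) is to be reviewed by the SRC".
- Section 9.2.2 asks for serious events arising after the reporting period to be passed to the sponsor if they are considered related to study drug and the investigator becomes aware of them.
- Section 9.2.3 makes the sponsor or its designee responsible for submitting suspected unexpected serious adverse reactions (SUSARs).

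**The concern.** A causality scale should give each event one class. Here the ordinary ambiguous event, one that starts on treatment and that the leukemia or another drug could also have caused, satisfies two adjacent definitions that fall on opposite sides of the related/unrelated line. Two investigators can each follow the text correctly and record different answers.

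Such events are unlikely to be rare in this population. Cytopenia, infection, bleeding and fatigue occurring on treatment in relapsed or refractory AML or MDS will often have a plausible disease explanation. The protocol itself expects disease to confuse the picture: Section 4.3.1 allows for out-of-range laboratory values attributed to the underlying disease, and Section 9.3 deals with uncertainty over whether an event is due only to the disease.

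At stake is the consistency of an input to safety decisions in a first-in-human part: what the SRC sees as drug-related when it reviews increments, what is weighed as a suspected reaction, and which late serious events are reported.

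**Working it through.** No sample size, power or error rate is involved, and the plan states no figure to reproduce. The check is one of logic on the two definitions, both of which are fully visible in Section 9.1.2.

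Let T mean that the timing is reasonable, and E that disease, other drugs or chemicals offer an alternative explanation. Then:

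- *Not related/unlikely related* = (not T) or E
- *Possibly related* = T and E

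| Timing reasonable (T) | Alternative explanation (E) | Meets *Not related/unlikely related* | Meets *Possibly related* |
|---|---|---|---|
| Yes | Yes | Yes | Yes |
| No | Yes | Yes | No |
| No | No | Yes | No |
| Yes | No | No | No |

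The first row is the only one that meets *Possibly related*, and it also meets *Not related/unlikely related*. So the overlap is not an edge case: (T and E) is wholly contained in ((not T) or E). Taken literally, *Possibly related* has no territory of its own.

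The fourth row goes to *Probably related* or *Definitely related* only if their further conditions on drug withdrawal or re-exposure are met. An event with reasonable timing, no likely alternative cause and no withdrawal information fits none of the four classes. This is a smaller gap, which the same rewording can close.

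Next, where the call enters and where it does not:

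- *Escalation.* Section 3.1.2.1 makes drug-related toxicity the trigger for SRC review of the maximum increase. The same section says that "dose escalation will only occur after discussion and agreement between the Sponsor and members of the SRC", and that "The exact dose increase and number of dose levels will be based upon the review of safety and, where available, PK, PD, and efficacy data". Relatedness is therefore one input to a decision taken on all the data.
- *Reporting.* Under Section 9.2.2, serious events within the reporting period go to the service provider within 24 hours whatever the causality. Relatedness decides only whether later serious events are passed on. It also bears on the SUSAR assessment in Section 9.2.3, because a SUSAR is by definition a suspected reaction.
- *Analysis.* The Part A primary endpoint in Table 4 counts AEs and serious AEs without a relatedness filter. Section 9.1.3 records every event regardless of cause, and Section 10.2.2.4 tabulates all treatment-emergent AEs. None of these changes with the call.

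**The case against.** The best defense of the wording is that the class labels guide the reader. The word *also* in *Possibly related* implies that the drug remains a candidate, while the other class is headed *unlikely related*, so a sensible investigator would keep it for events where the alternative is the better explanation. It can also be said that an explanation that is plausible is a stricter test than one that merely could apply. Both points have some force: the text leaves room for clinical judgement. But neither distinction is stated as a rule. Even if *plausible* is read as the stricter test, an event with good timing and a plausible disease cause still meets both definitions.

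Four stronger readings are tempting, and the documents do not support them.

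- A reader might infer that the relatedness call governs escalation. In the visible text it triggers only an SRC review of the increment, and every step needs agreement between the sponsor and the SRC. The Part A dose-limiting toxicity criteria are redacted and the SRC Charter is not among the documents, so which classes count as ONO-7475-related may be settled there.
- A reader might infer that a *Not related* call keeps an event out of expedited reporting. Serious events in the reporting period are sent in regardless of relationship, the sponsor or its designee processes them all, and Section 9.3 requires reporting where it is uncertain that disease is the only cause. Nothing visible makes the investigator's class alone decisive.
- A reader might infer that related-AE rates will be distorted between Part A and Part D, since Part D uses a different, two-class scale. No such comparison is planned, and Part D adds venetoclax.
- A reader might want a count of affected patients. The documents give no rate of such events and the cohort sizes are redacted, so any count would only restate its own assumptions.

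**Conclusion.** The defect stands as a flaw in a stated rule: the Part A causality classes are not mutually exclusive, and no visible text breaks the tie. Redaction does not explain it, because both definitions can be read in full.

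Its extent is logical rather than numerical. If the two descriptions of an alternative cause are taken as equivalent, all of *Possibly related* lies inside *Not related/unlikely related*; if *plausible* is taken as stricter, the overlap is smaller but still includes every event with reasonable timing and a plausible alternative cause. Events outside that group are not affected, so calling the classification arbitrary as a whole would go too far. That the group is common in this population is a judgement about the disease, not a figure from the documents.

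The consequence is moderate. The call feeds the SRC review of increments, SUSAR assessment and the reporting of late related serious events. It leaves the Part A primary endpoint and the treatment-emergent AE summaries untouched. The point should be corrected, but it does not threaten the validity of the Part A primary analysis.

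**What to change.** 1. Reword the Part A definitions in Section 9.1.2 so that each event fits exactly one class. In particular, a plausible alternative cause should not by itself place an event with reasonable timing in *Not related/unlikely related* when ONO-7475 also remains a plausible cause. Give a home to events with reasonable timing, no likely alternative and no withdrawal information. Carry the wording into the eCRF guidance.
2. Reconcile the reworded classes with the term ONO-7475-related in Section 3.1.2.1 and with the SRC Charter, so that all three use the term in the same way. Which classes should count toward the escalation trigger is for the sponsor and the SRC to state; this review does not propose a rule.
3. Query Part A events coded *Not related/unlikely related* despite plausible timing, and document any change of class.

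The cost is a few sentences of text, updated eCRF guidance and a small data review. The related-AE count may rise. Because the review would revisit causality after the fact in open-label data, the original and the revised class should both be kept.
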